1. INTRODUCTION

This document is the second addendum to the statistical analysis plan for the analysis of the US WorldMeds, LLC study USWM-LX1-3003-1. The original statistical analysis plan was dated 18-Jun-14 and amendment number 1 was dated 24-Dec-14.

All decisions were taken prior to database lock.

2. CHANGES TO EXISTING ANALYSIS PLAN

Change 1

Section 6.2 Derived Data

Questionnaire Data

The following sentence was revised in bold:

In the event that component items used to calculate total scores for questionnaire data e.g. SOWS Gossop score are missing, then the total scores will be computed as the average of the nonmissing item scores multiplied by the total number of items (e.g. multiply by 10 for the SOWS-Gossop) comprising the total score. This same method will be applied to all other questionnaire data to calculate total scores in a similar fashion.

Justification

To minimize the number of patients with missing total assessment scores due to missing single component items. This solution incorporates comments from the US Food and Drug Administration (FDA) in relation to the calculation of total scores based on non-missing item scores.

Change 2

Section 6.3 Analysis Populations

The following sentence was added in bold:

Effective: 22-Jan-2015

Page 3 of 11

The Enrolled Population includes all subjects screened into the study irrespective of whether they received the study medication.

Three principal analysis populations are defined as follows:

- Intent-to-treat (ITT), consisting of all randomized subjects. Subjects will be assigned for analysis according to the group to which they are randomized.
- Modified intent-to-treat (mITT), consisting of all subjects in the ITT group who received at least one dose of study medication. Subjects will be assigned for analysis according to the group to which they are randomized.
- Safety consisting of all subjects who received at least one dose of study medication. Subjects will be assigned for analysis according to treatment received.

Justification

To further clarify the definition of the safety analysis population.

Change 3

Section 6.9.2 Sensitivity Analysis

The following text will be added:

Additionally, further efficacy analysis will be conducted using the area under the curve (AUC) from Days 1 through 7 of the SOWS-Gossop scores as the endpoint. The AUC will be calculated on the original scale of measurement based on the back-transformed log scale estimates from the pattern mixture analysis. The LS means of the daily SOWS-Gossop scores (Days 1 through 7) will be exponentiated to get the geometric mean SOWS-Gossop score for each day. These back-transformed scores will then be used to calculate the AUC using the trapezoidal rule. AUC summary statistics will be reported, no formal statistical analysis will be performed.

Justification

The additional analysis was added to incorporate comments from the US Food and Drug Administration (FDA) regarding an additional proposed efficacy analysis. Since statistical inference on the AUCs, such as confidence intervals, would be difficult and the results at best

Effective: 22-Jan-2015

Page 4 of 11

approximate, due to the fact that a propagation of errors approach would be needed to accommodate the exponentiation of results from the log scale of measurement back to the original scale; we have elected to present the estimated AUC values as descriptive statistics.

Change 4

Section 6.10 Secondary Endpoint

The following text was amended:

The secondary efficacy endpoint is the completion status (i.e., whether a subject receives at least one dose of study medication on Day 7 and completes the 3.5-hour post-dose SOWS-Gossop assessment on Day 7). The proportion of subjects in each treatment arm who receive at least one dose of study medication on Day 7 and complete the 3.5-hour post-dose SOWS-Gossop assessment on Day 7 will be analyzed using a logistic regression model including fixed effects for treatment group and gender using the mITT population. One test will compare the 3.2 mg lofexidine group to placebo; a second will compare the 2.4 mg Lofexidine group to placebo. A sensitivity analysis will be performed on this endpoint using the ITT population.

Justification

Gender was inadvertently removed as a variable from the logistic regression model.

Change 5

Section 6.2 Assessments Recorded at Discontinuation Visit

Add the following text related to handling assessments recorded on discontinuation visit:

On days where a discontinuation visit is recorded on the same day as a scheduled visit, then the **scheduled visit** should be used be for analysis purposes and the discontinuation visit will be ignored. If a discontinuation visit is recorded on a study day where no scheduled visit is recorded, then it should be assigned to the **actual study day** the visit was recorded.

Justification

Effective: 22-Jan-2015

Page 5 of 11

To further clarify a set of rules for how to handle assessments recorded on the date of discontinuation instead of the scheduled study visit.

Change 6

Section 6.9.1 Principal Analysis

The following text in bold has been revised:

A pattern-mixture approach⁵ will be used in assessing SOWS-Gossop from Days 1 to 7 inclusive using the mITT population.

It will be assumed that subjects randomized to lofexidine who withdraw from the study will have a time trajectory comparable to placebo post withdrawal. The pattern-mixture model will be implemented using multiple imputations (Ratitch⁶, 2011). The imputation of missing values and the analysis will be performed multiple times (20 imputed datasets) with the initial seed value set at '123', and the inference of this sensitivity analysis will be based on the combined estimates using the standard multiple imputation technique. This method is detailed in the section entitled "Pattern-Mixture Model with Control-Based Pattern Imputation" (Ratitch⁷, 2013). Briefly, the initial step is to impute the relatively rare, non-monotone missing data via the MCMC Option of SAS® PROC MI. The imputation model will include as predictors an indicator variable for gender (1 d.f.), two indicator variables for treatment (2 d.f), the Baseline value, and variables for Day 1 through Day 7 data. This step uses iterative methods, with which nonconvergence is a possibility; should an MCMC imputation step not converge, alternative models will be developed by dropping time point variables from the model, one at a time starting at Day 7, until convergence is achieved. For example, if non-convergence occurs for the model that includes all the time point variables from baseline through Day 7, the next model to be considered will have all time point variables from baseline through Day 6, as well as the indicators for treatment and gender. The next model, if needed, would have all time point variables from baseline through Day 5, and so forth. Should this approach not succeed, ad hoc methods to impute non-monotone missing data will be developed and documented.

These contingency models for non-convergence, as well as the modeling of data with a monotone missing pattern, will require additional random number seeds. As stated in the SAP, the seed for the first step of the monotone missing imputation is '234'. The following additional seeds are to be used in the order shown for any additional modeling of non-monotone missing data as well as for the subsequent imputation of monotone missing data.

Effective: 22-Jan-2015

Page 6 of 11

Protocol Number USWM-LX1-3003-1 Statistical Analysis Plan Addendum 2 Version: Final Issue Date: 22-Jan-2015

- 1. 345
- 2. 456
- 3. 567
- 4. 678
- 5. 789
- 6. 890
- 7. 901
- 8. 012
- 9. 124
- 10.245
- 11.356
- 12.467
- 13. 578
- 14.689
- 15.790
- 16.145
- 17.256
- 18.367
- 19.478
- 20.589

Effective: 22-Jan-2015

Page 7 of 11

Justification

To acknowledge the possibility of non-convergence and to clarify a process to implement systematic adjustments to the model to achieve convergence. To simplify the imputation model by modeling the entire data set once rather than for each separate combination of treatment and gender. To pre-specify a list of random number seeds for use in the imputation process.

Effective: 22-Jan-2015

Page 8 of 11

Effective: 22-Jan-2015

Page 9 of 11

Effective: 22-Jan-2015

Page 10 of 11

Approval for implementation of

Fitle:	A Phase 3, Randomized, Multicenter, Double-Blind, Placebo-Controlled, Efficacy, Safety and Dose-Response Study of Lofexidine in the Treatment of Opioid Withdrawal (Days 1-7) Followed by Open-Label, Variable Dose Lofexidine Treatment (Days 8-14)
Reference:	USWM-LX1-3003-1/SAP Addendum/1
Addendum No:	2
Date effective:	22-Jan-2015
Author:	Principal Statistician
reviewer:	Principal Statistician
Author's signature:	Date:
Reviewer's signature:	Date:
The above Statistical Ar Sponsor:	nalysis Plan Addendum has been reviewed and approved by the
Name of Approver: Position:	Medical Director, US WorldMeds, LLC
Signature:	Date:
Name of Approver:	
Position:	Sr. Manager, Biometrics, US WorldMeds, LLC
Signature:	Date:

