## 15.4 Efficacy Assessment Methods

### 15.4.1 Short Opiate Withdrawal Scale (SOWS-Gossop)

The SOWS-Gossop [16] will be completed by the subject at baseline (before randomization), once daily at 3.5 hours ( $\pm$  10 minutes) after the first dose of study medication on Days 1-7, and once daily before dosing on Days 8-14. Note that at the time of each daily evaluation, subjects should consider their symptoms over the last 24-hour period or since the last time the subject took this test. Also, this scale should be completed before completion of the OOWS-Handelsman, MCGI, VAS-E, and COWS.

The SOWS-Gossop scale assesses subjective symptoms of opioid withdrawal ([Appendix 1](#)). It is a subject-rated scale consisting of 10 items that are scored on a 4-point scale of 0 = none, 1 = mild, 2 = moderate, and 3 = severe (minimum score of 0, maximum score of 30) (see [Table 2](#) below). The overall score will be the simple sum of the 10-item scores. Lower observed values in SOWS-Gossop scores indicate a more positive clinical outcome.

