6.2 Derived Data

• Definition of baseline

For all variables, baseline is defined as the last non-missing value prior to the receiving the first dose of study medication.

All tabulations involving change from baseline data will only include subjects with cohort data i.e. with data at baseline and at follow-up. Change from baseline will be calculated as follow-up values minus baseline value.

• Incomplete dates

All incomplete dates will be included in the clinical database as they were entered in the eCRF. Thereafter for calculation purposes, the incomplete dates will be completed using pre-defined rules. If a day or month is not recorded it will be replaced by the first day of the month or January respectively, provided this does not contradict any other dates recorded. For missing adverse events and medications dates/times during the trial, the worst-case date will be used (e.g. the end of the month for a stop date and 23:59 for the stop time, the date/time of initial dose for start of AE i.e. all events with missing start dates will be assumed to be treatment emergent).

• Ambiguous values

In the case where a variable is recorded as ">x", " \geq x", "<x" or " \leq x", then for analysis purposes a value of x will be taken. Where a range of values is quoted the midpoint of the range will be taken.

Effective: 14-Feb-13

Page 6 of 26

• Questionnaire Data

In the event that component items used to calculate total scores for questionnaire data e.g. SOWS Gossop score are missing then the total scores will also be set to missing.

• Site pooling for statistical analyses

For the purposes of statistical analyses models where site is included within the model as a fixed effect, sites randomizing < 6 subjects will be pooled from smallest to largest until the pooled site subsequently created has at least 6 subjects. In the event that the pooling of sites with less than 6 subjects does not result in a site with > 6 subjects, then that pooled site with < 6 subjects will also be pooled with the next largest site with > 6 subjects. To break ties if more than one site has the same number of subjects, the site identifier will be used as a secondary sort key.

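### SAP Addendum 2 prorates questionnaire totals from any number of answered items, so a nearly blank SOWS-Gossop form enters the primary analysis as an observed score; a minimum number of answered items is needed.

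*SAP*

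**What the plan says.** Protocol Section 15.4.1 describes SOWS-Gossop as 10 items, each scored 0 to 3: "The overall score will be the simple sum of the 10-item scores". The SAP of 18 June 2014, Section 6.2, was strict about incomplete forms: if component items "are missing then the total scores will also be set to missing".

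SAP Addendum 2 (22 January 2015), Change 1, replaced that rule. For an incomplete form it says that "the total scores will be computed as the average of the nonmissing item scores". That mean is then scaled up to the full length of the form, a factor of 10 for SOWS-Gossop. The scope is general: "This same method will be applied to all other questionnaire data to calculate total scores in a similar fashion". The reason given is narrower than the rule: "To minimize the number of patients with missing total assessment scores due to missing single component items". The justification adds that the solution incorporates FDA comments on computing totals from answered items.

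Neither Change 1 nor any other part of the documents states a minimum number or share of answered items. No flag for prorated totals and no sensitivity analysis of this rule is planned.

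**The concern.** The rule does more than its justification asks. With one item missing out of ten, proration is accurate and sensible. With nine missing out of ten, one answer is multiplied by ten and stands for the whole scale. A form on which only yawning is marked, as severe, scores 30 of 30. A form on which only runny eyes is marked, as none, scores 0.

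Three features of the plan carry such a score into the primary result:

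- The principal analysis (Addendum 1, Change 7, revised by Addendum 2, Change 6) imputes only missing values, first the non-monotone and then the monotone gaps. A prorated total is not missing, so neither step touches it.
- The same value is used as a baseline or daily predictor when other days are imputed.
- The analysis is on the natural log of the score plus 1, where a spurious 0 is an extreme value.

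Addendum 2, Change 5, also assigns a discontinuation-visit form to its actual study day when no scheduled visit is recorded. A nearly blank form on that day would count as an observation and displace the control-based imputation.

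**Working it through.** The documents give no numerical result for this rule, so there is no figure to reproduce. The check applies the rule directly and then uses simulation under stated assumptions.

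**Inputs from the documents.** 10 items scored 0 to 3 (Protocol 15.4.1); 13 signs scored 0 or 1 for OOWS-Handelsman (Protocol 15.4.2); multiplier equal to the number of items (Addendum 2, Change 1); analysis scale ln(score + 1) (Addendum 1, Changes 6 and 7).

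**Exact bounds.** Let k items be answered with sum S.

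- Prorated total = 10 × S / k. The true total lies between S and S + 3 × (10 − k), so the largest possible error is 3 × (10 − k) points.
- For k = 1 the total is 0, 10, 20 or 30, which is 0, 2.398, 3.045 or 3.434 on the log scale.
- Worst cases at k = 1: a lone answer of 3 gives 30 when the full form could sum to 3 (ln 31 = 3.434 against ln 4 = 1.386). A lone answer of 0 gives 0 when the full form could sum to 27 (ln 1 = 0 against ln 28 = 3.332).
- For OOWS-Handelsman, one answered sign gives 0 or 13.

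**Typical error (assumed model).** 100,000 forms were simulated. Items were cut from a normal model with one common factor, items were missing at random, and two severity levels were used (mean totals about 5.3 and 11.1, SD 5.1 and 7.0).

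| Items answered | Largest possible error | RMSE of total | Mean error in ln(score + 1) |
|---|---|---|---|
| 1 | 27 | 6.7 to 8.4 | −0.53 to −0.55 |
| 3 | 21 | 3.4 to 4.3 | −0.14 to −0.19 |
| 5 | 15 | 2.2 to 2.8 | −0.06 to −0.09 |
| 7 | 9 | 1.5 to 1.8 | −0.02 to −0.04 |
| 9 | 3 | 0.7 to 0.9 | about −0.01 |

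**Compared with setting the total to missing.** The alternative is to predict the day's score from the subject's other days. The documents give no day-to-day correlation r, so 0.5 to 0.7 is assumed. The simulated SD of the log score was 0.90 and 0.75. From one neighbouring day the prediction error is SD × √(1 − r²):

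- r = 0.5: 0.90 × 0.866 = 0.78 and 0.75 × 0.866 = 0.65
- r = 0.7: 0.90 × 0.714 = 0.64 and 0.75 × 0.714 = 0.54

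Allowing for prediction from adjacent days more generally, the simulated range was about 0.4 to 0.8. Under similar item assumptions, the log-scale RMSE of proration was:

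- 1 to 2 items answered: 0.76 to 1.34, bias −0.21 to −0.63, which is worse than prediction;
- 5 to 7 items answered: 0.22 to 0.47, bias −0.02 to −0.09, which is about as good or better.

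The crossover therefore lies somewhere between these two groups.

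**Effect on an arm mean (assumed frequency).** If 1% of an arm's forms had a single answer, a mean error of −0.5 per such form would move that arm's mean log score by 0.01 × 0.5 = 0.005.

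**The case against.** The strongest reply is that the problem may never arise. Days 1 to 7 are inpatient, with one 10-item form a day at a fixed time. Incomplete data generate queries (Protocol 18.2) and missing data go back to the site (Protocol 21), although a query may not recover a subject's own rating. The stated target is a single missing item, where the error is at most 3 points. The rule was also fixed before database lock. All of this stands, and it keeps the point minor. It does not explain why the rule is written more widely than its purpose.

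A second reply is that setting a total to missing is not neutral. Monotone gaps on lofexidine are imputed from placebo data, so a strict floor would replace a subject's own answers with a placebo-based draw. A single imputed draw also has about 1.41 times the error of the predicted mean. This also stands, and it argues for a low floor. A reader might infer that a conventional 80% rule (8 of 10) is required. The figures above do not support that, because forms with 5 to 7 answers carry good information and would be lost.

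A reader might also infer that the agency's comment leaves room for a floor. The comment itself is not in the documents, only a one-line paraphrase, so that cannot be confirmed either way.

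**Conclusion.** The point holds as a minor defect in a stated rule. Proration without a floor goes beyond its own justification and lets a one-item form stand as an observed SOWS-Gossop score, with an error of up to 27 points. That bound follows from the documents alone. The typical-error figures and the comparison with imputation rest on assumed item and day-to-day correlations, and the bounds and typical-error table are for a 10-item, 0-to-3 scale.

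It is tempting to read the negative log-scale error as a downward bias in the primary endpoint. The documents do not support that reading. The endpoint in Addendum 1, Change 6, is a difference between arms, and nothing in the plan suggests that nearly blank forms would be more common in one blinded arm. Equally frequent error would largely cancel. With the frequency of such forms unknown, the effect on the primary result is unquantified and probably small.

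**What to change.** In SAP Section 6.2 as revised by Addendum 2, Change 1, prorate a total only when at least half of the items are answered: 5 of 10 for SOWS-Gossop and 7 of 13 for OOWS-Handelsman. Otherwise set the total to missing so that, for SOWS-Gossop, the planned multiple imputation handles it. Report the number of prorated totals by arm and study day, which would show whether the issue arose at all.

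The cost is one clause and one table. The downside is a few more missing totals, and those in monotone gaps on lofexidine would be imputed from placebo data. A somewhat lower floor could also be defended; what matters is that one is stated.

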6.9.1 Principal Analysis

A pattern-mixture approach⁵, with subjects stratified by disposition within Days 1-7, will be used in assessing SOWS-Gossop AUC (1-7). The 4 disposition strata are as follows:

- Subjects who complete Days 1-7 of the study (i.e. receives at least one dose of study medication on Day 7 and completes the 3.5-hour post-dose SOWS-Gossop assessment on Day 7);
- Subjects who discontinue due to lack of efficacy (including adverse events related to opioid withdrawal);
- Subjects who discontinue due to adverse events related to intolerability or toxicity to study drug; and
- Subjects who discontinue for other reasons.

The inference is comprised of several steps. The first two rely on standard statistical software and a commonly-used type of statistical model. The remaining three rely on matrix manipulations. Additionally, the last step appeals to the statistical delta method (propagation of errors).

- 1. Transformation. Because of the inherent skewness in the SOWS-Gossop scores the raw data will first be transformed to the natural logarithm of the score plus 1.0.
- 2. Modelling. A linear mixed effects repeated-measures model will be constructed for the SOWS-Gossop score. The fixed effects will be disposition stratum, treatment and time, and their respective two-way and three-way interactions, as well as a main effect of gender (randomization stratification factor) and baseline (pre-dose) SOWS-Gossop score as a one degree of freedom covariate. For each combination of treatment and stratum, the time course will be modelled as a linear change point model, allowing for one slope between Days 1 and 2 and a possibly different slope from Days 2 through 7. The model will parameterized to ensure that the predictions from the two line segments agree at Day 2. Subjects will be treated as a random effect, and the slope and intercept parameters will be treated as random coefficients. Modelling the time course, rather than using each time point as a discrete level of a model factor, allows estimation of group means through Day 7 even in the non-completer strata. The choice of Day 2 as the change point is based on prior lofexidine studies, in which SOWS-Gossop mean scores in the placebo group increased from Day 1 to Day 2 and then decreased through Day 7. The modelling allows a different time course for each of the lofexidine dose groups.

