- 3. Point estimates of AUC (1-7). For each combination of disposition stratum, treatment and study day, the estimated least squares means SOWS-Gossop (on the log scale) for males and females will be combined using a weighted average, the weights being the relative proportions of males and females in the mITT population for each of the 12 stratum. The results will then be transformed back to the original SOWS-Gossop scale of measurement, from which point estimates of AUC (1-7) for each combination of stratum and treatment will be computed using the linear trapezoidal rule. It should be

Effective: 14-Feb-13

Page 13 of 26

noted that these calculations will not be derived from AUC(1-7) computed within individual subjects, many of whom will have incomplete data for the later study days in Days 1-7. In particular, there will be no imputation of data for individual subjects.

- 4. Estimates of treatment effect. For each active treatment, the treatment effect (lofexidine 3.2 mg versus placebo or lofexidine 2.4 mg versus placebo) will be estimated with respect to AUC (1-7) within each disposition stratum. Then a weighted average of treatment effects will be computed, where the weights are the relative proportions of subjects in the 4 strata.
- 5. Interval estimates of AUC (1-7) and hypothesis testing. The covariance matrix of the mixed model's estimated fixed effects will be used with standard linear model methods to derive the covariance matrix of the weighted average of male and female log-transformed SOWS-Gossop scores. The multivariate delta method (Ku, 1966; NIST/SEMATECH e-Handbook) will be used to derive the covariance matrix of the back-transformed SOWS-Gossop time course. Standard linear model methods will then be used to derive the covariance matrix of the weighted average of AUC (1-7) treatment effects, from which confidence intervals and p-values will be derived.

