It will be assumed that subjects randomized to lofexidine who withdraw from the study will have a time trajectory comparable to placebo post withdrawal. The pattern-mixture model will be implemented using multiple imputations (Ratitch⁶, 2011). The imputation of missing values and the analysis will be performed multiple times (20 imputed datasets) with the initial seed value set at '123', and the inference of this sensitivity analysis will be based on the combined estimates using the standard multiple imputation technique. This method is detailed in the section entitled "Pattern-Mixture Model with Control-Based Pattern Imputation" (Ratitch⁷, 2013). Briefly, the initial step is to impute the relatively rare, non-monotone missing data via the MCMC Option of SAS® PROC MI. This step uses iterative methods, with which non-convergence is a possibility; should an MCMC imputations that converge will be used in the analysis. This imputation model will be implemented for each combination of gender and treatment. (It should be noted that by performing the imputation for each such combination, the imputation modelling will be richer than the model used to inferentially analyse the data. It is acceptable, even preferable, for the imputation model to be richer than for the analysis model (see Little and Rubin, 2002).

The next step applies to the monotone missing data. The values for each pattern will be imputed using the chained equation method by SAS® PROC MI option MONOTONE REG. This MNAR imputation employs only the appropriate data for each pattern. That is, the missing data for lofexidine treatment arm at time t will be imputed using only the data on placebo subjects up to time t and the data for lofexidine subjects who have data up to time t-1 but are missing data at time t. The model for imputing missing data at time t will include fixed effect terms for study day from the baseline visit through to the t-1 visit and sex. Note that a term for treatment group is not included in this imputed data sets will be analyzed using the MMRM model described below and then summarized using PROC MIANALYZE. The model will include fixed effects for treatment group, baseline log_e (SOWS-Gossop score +1), sex, study day (days 1-7), and

Effective: 24-Dec-2014

Page 7 of 29

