treatment group-by-day interaction. In this model the treatment group term in the model represents the effect of treatment over days 1 to 7. An unstructured covariance model will be used. However, in the event that this model does not converge then the following covariance models will be used in order until the model converges: Toeplitz, first-order autoregressive and compound symmetry. Analysis will be performed using PROC MIXED in SAS and the resultant F-tests will be based on Kenward-Roger's adjusted degrees of freedom.

Justification

Fitting an MMRM analysis without the imputation described above would have entailed an assumption that the missing data are missing at random (MAR). The combined process of imputation followed by MMRM does not assume MAR and provides an unbiased estimate of the treatment effect that follows under the assumption that the mechanism by which data are missing not at random (MNAR) is that upon withdrawal from the study, the SOWS-Gossop trajectory of subjects randomized to lofexidine evolves as the trajectory of placebo subjects.

Change 8

Section 6.9.1 Sensitivity Analysis

The text in bold has been edited:

The following sensitivity analyses will be conducted:

- \neq The above analysis will be performed using the per-protocol population.
- ≠ The log_e (SOWS-Gossop score plus 1) from day 1 to day 7 will be analyzed using a MMRM model on the mITT population.

The model will include fixed effects for treatment group, baseline log_e (SOWS-Gossop score plus 1), sex, study day (days 1-7) and treatment group-by-day interaction. In this model the treatment group term in the model represents the effect of treatment over days 1 to 7. An unstructured covariance model will be used. However, in the event that this model does not converge then the following covariance models will be used in order until the model converges: Toeplitz, first-order autoregressive and compound symmetry. Analysis will be performed using PROC MIXED in SAS and the resultant F-tests will be based on Kenward-Roger's adjusted degrees of freedom. This MMRM analysis assumes that the missing data are missing at random (MAR). This analysis provides an unbiased estimate of the treatment effect that would have been observed had all subjects continued

Effective: 24-Dec-2014

Page 8 of 29

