An MMRM model will be used to test for a difference in the log_e (SOWS-Gossop score +1) at each of days 1, 2, 3, 4, 5, 6, and 7 between the 3.2 mg Lofexidine group and placebo and between the 2.4 mg Lofexidine group and placebo. The model will include fixed effects for treatment group, baseline log_e (SOWS-Gossop score +1), sex, visit (day 1, day 2, day 3, day 4, day 5, day 6 and day 7) and treatment-by-visit interaction. An unstructured covariance model will be used. However, in the event that this model does not converge then the following covariance matrix will be used in order until the model converges: Toeplitz, first-order autoregressive and compound symmetry. Analysis will be performed using PROC MIXED in SAS and the resultant F-tests will be based on Kenward-Roger's adjusted degrees of freedom.

Effective: 24-Dec-2014

Page 10 of 29

Justification

The primary analysis no longer includes site in the model; therefore site has been removed as a variable from all subsequent statistical models.

Change 11

Section 6.11 Tertiary/Exploratory Endpoints

Amend the following text related to OOWS-Handelsman, MCGI (Subject and Rater), VAS-E, and COWS

The same methods used for SOWS-Gossop detailed above on days 1, 2, 3, 4, 5, 6, and 7 will be used for OOWS-Handelsman, MCGI (Subject and Rater), VAS-E, and COWS scores on days 1, 2, 3, 4, 5, 6, and 7. Depending on the distribution of these outcomes data transformations maybe used to normalise the data. Any transformation will be specified within the SAP prior to database lock.

The text in bold was added to the following:

The same methods used for SOWS-Gossop detailed above on days 1, 2, 3, 4, 5, 6, and 7 will be used for OOWS-Handelsman, MCGI (Subject [Severity of opiate withdrawal and side effect index separately] and Rater [Severity of illness and side effect index separately], VAS-E, and COWS scores on days 1, 2, 3, 4, 5, 6, and 7, where the baseline covariate will be the baseline value of the endpoint under analysis. The same model will be used for MCGI [Subject and Rater] and VAS-E, except that there will be no baseline covariate as these endpoints do not have a baseline measurement. Depending on the distribution of these outcomes data transformations maybe used to normalise the data. Any transformation will be specified within the SAP prior to database lock.

Justification

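### The AUC(1-7) rule in SAP Addendum 2 exponentiates log_e(score+1) means without subtracting 1; followed as written, every arm's descriptive AUC is 6 score-days too high

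*SAP*

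**What the plan says.** SAP Section 6.9.1, step 1 sets the modelling scale: "the raw data will first be transformed to the natural logarithm of the score plus 1.0". Addendum 1 rewrites the principal analysis but keeps the offset wherever it spells out the transform: in the baseline covariate of the new principal model (Change 7), in the outcome of the sensitivity MMRM and of the tipping-point analysis (both Change 8), and in the daily analysis (Change 10: "An MMRM model will be used to test for a difference in the log_e (SOWS-Gossop score +1) at each of days").

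Addendum 2, Change 3 adds a descriptive AUC(1-7) to Section 6.9.2, built from the pattern-mixture estimates. It states the scale: "The AUC will be calculated on the original scale of measurement". It then states the operation: the daily LS means "will be exponentiated to get the geometric mean SOWS-Gossop score for each day", and those values go into the trapezoidal rule. Its justification again describes the step as "exponentiation of results from the log scale of measurement back to the original scale". Neither place mentions subtracting 1.

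The AUC step that Addendum 1 replaced (Section 6.9.1, step 3) named no operation: "The results will then be transformed back to the original SOWS-Gossop scale of measurement". Addendum 1, Change 1 asks for back-transformed LS means from all log-scale models and gives no formula either.

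Protocol Section 15.4.1 and Table 2 give the score range as 0 to 30.

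**The concern.** The inverse of y = log_e(score+1) is exp(y) - 1. Change 3 promises an AUC on the score scale, yet the one operation it names stops short of that inverse and leaves every daily value 1 point too high. It also calls the result the geometric mean score, which it is not.

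A programmer who follows the sentence literally will report AUC levels that are not on the stated scale. Change 3 plans only summary statistics for this AUC, with no inference, so the reported levels are its whole output. AUC(1-7) was also the protocol's primary endpoint (Section 17.2.4) and the basis of its power calculation (Section 17.2.9), and the addendum says it was brought back in response to FDA comments. Readers are therefore likely to look at the levels and may form percent reductions from them.

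**Working it through.** The documents state no AUC value, so there is no figure to reproduce. The check is algebra plus a numerical confirmation.

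**Inputs**
- Modelled scale: log_e(score+1) (SAP 6.9.1 step 1; Addendum 1, Changes 7, 8 and 10).
- Written back-transformation: exp(LS mean) (Addendum 2, Change 3).
- Integration: trapezoidal rule on Days 1 to 7, that is 7 points and 6 one-day intervals.
- Score range: 0 to 30 (Protocol 15.4.1, Table 2).

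**Size of the error.** Let m_d be the LS mean on day d.
- As written: AUC_w = sum of w_d × exp(m_d).
- Full inverse: AUC_c = sum of w_d × [exp(m_d) - 1].
- Weights w_d: 0.5, 1, 1, 1, 1, 1, 0.5.
- AUC_w - AUC_c = 0.5 + 5×1 + 0.5 = **6 score-days**, in every arm and for any data.

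End points: score 0 on all days gives 6 as written and 0 with the full inverse; score 30 on all days gives 186 and 180.

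Numerical confirmation on simulated integer scores from 0 to 30, including zeros, for four assumed time courses (as written / full inverse): 37.879 / 31.879, 26.398 / 20.398, 14.084 / 8.084, 76.890 / 70.890. The gap is 6.000 each time.

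**Relative error in an arm's level.** This is 6/A, where A is the AUC from the full inverse. If the daily values lie within 0-30, A is at most 180, so the error is at least 6/180 = 3.3%. The documents give no arm means, so the levels below are assumed constants:

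| Daily level | Full inverse | As written | Excess |
|---|---|---|---|
| 5 | 30 | 36 | 20% |
| 8 | 48 | 54 | 12.5% |
| 10 | 60 | 66 | 10% |
| 15 | 90 | 96 | 6.7% |

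**Comparisons between arms.** With placebo AUC A and lofexidine AUC B:
- Difference: (A+6) - (B+6) = A - B, so the error is 0.
- Percent reduction: (A-B)/(A+6) instead of (A-B)/A, so it keeps the fraction A/(A+6). At A = 180 that is 180/186 = 0.968, so the reduction is understated by at least 3.2% of its value.

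Illustration with two assumed profiles over Days 1-7:
- Placebo 8, 10, 9, 8, 7, 6, 5: AUC 4+10+9+8+7+6+2.5 = 46.5, or 52.5 as written.
- Lofexidine 7, 8, 6, 5, 4, 3, 3: AUC 3.5+8+6+5+4+3+1.5 = 31.0, or 37.0 as written.
- The difference is 15.5 both ways. The percent reduction is 15.5/46.5 = 33.3% against 15.5/52.5 = 29.5%.

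**Label.** Take scores 0, 3 and 8. Then exp(mean of log_e(score+1)) = (1×4×9)^(1/3) = 36^(1/3) = 3.30. Subtracting 1 gives 2.30. The geometric mean of the scores themselves is 0. Neither back-transformed value is the geometric mean score.

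**The case against.** **The subtraction may be understood.** Change 3 places the AUC on the original measurement scale and calls the daily values back-transformed. Exponentiation alone can never return the scale minimum of 0, so the word could be shorthand for inverting the stated transform. This reading is reasonable, and it is why the point is an error in the written rule and not evidence of a programming error. It does not supply the missing step: no sentence in the SAP or its addenda gives the inverse, and the justification repeats exponentiation alone.

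**The +1 on the revised outcome is partly inferred.** Addendum 1 replaced the section that defined the transform, describes the new endpoint only as log-transformed, and writes the +1 in the principal model only for the baseline covariate. That is so. However, the tipping-point analysis in Change 8 applies log_e(score+1) to the imputed outcome and then fits the primary MMRM, and scores of 0 require an offset. No passage gives the SOWS-Gossop outcome a different one.

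**A table shell might define the value.** The shells are not in the available text, and a footnote there could state the inverse. That would help, but it would not correct the sentence in Change 3.

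**The consequence is small.** This stands in full. The AUC is descriptive, differences between arms cancel, the primary test is on the log scale, and the SAP plans no percent reduction. The 3.3% and 3.2% floors assume the maximum score on every day, and they and the 6-186 range assume back-transformed values within 0-30, although the regression imputation has no stated bounds.

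**Conclusion.** The concern holds as a minor error in the written rule. Followed literally, Addendum 2, Change 3 gives an AUC(1-7) exactly 6 score-days too high in each arm and attaches a wrong label to the daily values. The 6 does not depend on the data; it rests on unit-spaced days from 1 to 7 and on an offset of 1 in the modelled outcome. The relative error depends on arm means that the documents do not give. Absolute AUC differences, the primary test and the power calculation are unaffected. Nothing here shows that the analysis was programmed wrongly.

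**What to change.** In Addendum 2, Change 3, state that each day's back-transformed value is exp(LS mean) - 1, that is, the geometric mean of (score+1) minus 1, and that these values enter the trapezoidal rule. Word the justification to match. Replace the geometric-mean label, for example with: back-transformed LS mean, exp(LS mean) - 1. State that the same inverse applies to the back-transformed SOWS-Gossop LS means required by Addendum 1, Change 1.

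The cost is one line of SAP text, a table label and a check that the program subtracts 1. No new data or analysis is needed.
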